6.2 Safety evaluation

APRV is a mode of MV for ARDS patients and has been shown to be safe in animal and clinical studies.

7. Adverse events and severe adverse events

Adverse event reports: Adverse medical events that occur in patients receiving APRV, but are not necessarily causally related to treatment.

Reports of serious adverse events: patients receiving APRV experienced events requiring prolonged hospitalization, disability, incapacity to work, life-threatening events or death.

During a clinical trial, the clinical investigators are obligated to take necessary measures to ensure the safety of the patients and to document them timely. If serious adverse events occur during the clinical trial, the investigators should immediately administer appropriate treatment to the subject, and investigators should report to clinical trial unit Ethics committee, provincial or regional food and drug administration and state food and drug administration and sponsor by telephone or fax within 24 hours. At the same time, a written report shall be submitted to the above institutions within 15 days. The serious adverse event that occurred during study must be completed serious adverse event report form on the CRF.

All serious adverse events should be followed up until resolved and returned to baseline. Medical documentation of serious adverse events that proved to be irresolvable/permanent conversion to other treatment or death should be documented in the original documentation and follow-up form as well as results of laboratory and other tests.

The investigators and other responsible persons should analyze and determine the causal relationship between serious adverse events in the

subjects from a clinical perspective.

8. Statistical analysis and methods

Statistical analysis was performed by Prism 4.01. Due to the parameters are abnormal distributed, the data is showed as median (interquartile range).The data obtained at each step were compared using Friedman ANOVA of repeated measurements and, when appropriate, through Dunn post hoc tests using Bonferroni correction.Qualitative data were compared with Fisher's exact test.All comparisons were two-sided, $P < 0.05$ indicates the existence of significant difference.

9. Medical treatment and protection of subjects

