- (3) physiological and laboratory test: Blood routine, Serum biochemical examination (total protein, albumin (ALB), total bilirubin (TB), aspartate aminotransferase (AST), alanine transaminase (ALT), gamma-glutamyl transpeptidase (GGT), blood urea nitrogen (BUN), serum creatinine (Scr)),

brain natriuretic peptide (BNP), C-reactive protein (CRP), respiratory mechanics, cardiac and hemodynamic status at the time of before APRV, APRV 24h, ARPV 48h and APRV 72h.

3.2 sample size

Referring to previous literatures, the number of patients is generally required to be 20, and the number of patients should be increased to 30 in consideration of shedding and withdrawal.

4. Study population

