4.2 Inclusion criteria

The following three items must be met simultaneously:

- (1) Age: >18 years old and <80 years old
- (2) ARDS was diagnosed as moderate to severe according to the 2014 Berlin definition.
- (3) APRV duration is expected to exceed 72 hours.

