4.3 Exclusion criteria

Any of the following exclusion criteria is an exclusion:

- (1) APRV contraindications including pneumothorax, severe COPD, severe asthma, and intracranial hypertension
- (2) Pregnancy and perinatal stage
- (3) Severe cardiac dysfunction (NYHA class III or IV, acute coronary

syndrome or persistent ventricular tachyarrhythmia), chronic cardiopulmonary disease resulting in enlargement of the right heart, cardiogenic shock or cardiac perioperative period

(4) Refractory shock

(5) BMI > 35 kg/m²

5. The items and frequency of clinical and laboratory examinations to be performed

Pulmonary gas distribution, pulmonary shunt, and V/Q ratio were monitored by EIT before APRV and 2h, 6h, 12h, 24h, 48h and 72h after APRV. Blood routine, serum biochemistry test, BNP, CRP and arterial blood gas were recorded before APRV and 24h, 48h and 72h after APRV. cardiac status was monitored by point-of-care ultrasound.

6. Evaluation

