6.1 Primary and secondary outcome

Primary outcome: the effect of 24h APRV on pulmonary gas distribution monitored by EIT.

Secondary outcome: the effect of APRV on V/Q and pulmonary shunt at each time point monitored by EIT.

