9.2 Medical treatment and protection of subjects during the study

The rights and welfare of the subjects will be protected during the

study, and the quality of their medical care will not be affected by their refusal to participate or withdrawal from the study.

If the patient drops out of the study, we will no longer conduct study related tests.

The investigators will provide insurance for the subjects participating in the study program. If the subjects suffer any damage related to the study, they will receive timely free treatment and be compensated or compensated according to laws and regulations and mutual agreements.

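### The only repeated-measures test named needs all seven EIT readings, so patients with valid baseline and 24h data but no 48h or 72h reading drop out of the 24h primary comparison

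*Protocol*

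**What the plan says.** Section 6.1 of the protocol sets the primary outcome as "the effect of 24h APRV on pulmonary gas distribution monitored by EIT". Section 5 lists the readings: gas distribution, shunt and V/Q are "monitored by EIT before APRV and 2h, 6h, 12h, 24h, 48h and 72h after APRV". That is seven steps, and Section 3.1 gives the same list.

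Section 8 names one method for repeated quantitative data: "The data obtained at each step were compared using Friedman ANOVA of repeated measurements" and, "when appropriate, through Dunn post hoc tests using Bonferroni correction". Fisher's exact test is for qualitative data only. No separate baseline-to-24h test is named. All tests are two-sided at 0.05.

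Three other places bear on whether the later readings will be complete:

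- Section 3.2 takes 20 patients as required and says "the number of patients should be increased to 30 in consideration of shedding and withdrawal".
- Section 9.2 says "If the patient drops out of the study, we will no longer conduct study related tests".
- Section 4.2 requires for entry only that "APRV duration is expected to exceed 72 hours".

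**The concern.** Friedman's test ranks each patient's values across all steps. A row with a missing value cannot be ranked, so the patient is left out. Dunn's contrasts use the same ranks and do not bring that patient back. The tested 24h result therefore depends on remaining under study to 72h, which is settled after the endpoint has been measured.

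Two things are at stake. Valid 24h pairs are lost, which costs precision and power. The tested group may also be selected: death or deterioration after 24h would remove poor responders, and early improvement would remove good ones. The net direction cannot be known in advance. The median (interquartile range) summaries are not affected.

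**Working it through.** **Inputs from the protocol.** Seven EIT steps (Sections 3.1 and 5); primary time point 24h (Section 6.1); 30 patients enrolled against 20 required (Section 3.2); two-sided 0.05 (Section 8).

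**The plan's own figure.** The base of 20 comes from earlier literature without an effect size, SD or power, so it cannot be reproduced. The step from 20 to 30 fits a one-third loss, 20 / (1 − 1/3) = 30, or a simple 50% addition, 20 × 1.5 = 30. The protocol states neither rate.

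**Does the test drop these patients?** A 30 × 7 table with 48h and 72h missing in 10 rows gives an undefined Friedman statistic. It becomes computable only when those 10 rows are removed, leaving n = 20.

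**How many pairs are lost?** Loss rate and timing are assumed. With a constant loss rate over 72 hours, the number with 24h data is 30 × (n72/30)^(1/3).

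| Lost by 72h | With 24h data | All seven readings | Pairs discarded | Precision factor |
|---|---|---|---|---|
| 10% | 28.96, about 29 | 27 | 2 | √(29/27) = 1.04 |
| 20% | 27.85, about 28 | 24 | 4 | √(28/24) = 1.08 |
| 33% | 26.21, about 26 | 20 | 6 | √(26/20) = 1.14 |

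If the whole one-third loss fell after 24h, 30 − 20 = 10 pairs would be discarded. That is the most this rate allows.

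**How far could the tested group shift?** Simulation: among patients with 24h data, those with the lowest staying score are removed. The score correlates 0.3 / 0.5 / 0.7 with the 24h change (assumed, one direction). The shift in the completers' mean, in SD of the 24h change, is:

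- 29 to 27 patients: 0.04 / 0.07 / 0.09
- 28 to 24 patients: about 0.08 / 0.13 / 0.18
- 26 to 20 patients: 0.11 / 0.19 / 0.27
- 26 to 20 with three lost from each end: about 0

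**False positives.** Simulated with no true effect, 26 to 20 patients, the same three correlations, and equal independent normal noise at each step:

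- 24h Dunn contrast after a significant Friedman test: 0.2% / 0.6% / 2.2% with 21 comparisons, or 0.5% / 1.3% / 3.4% with 6. Not inflated.
- Overall Friedman test: 4.8% / 6.9% / 9.6%. It does exceed 5% when loss is related to response.
- Signed-rank test on all 26 pairs: 4.9% / 4.9% / 5.2%.

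**Power.** Assumed: a sustained change of 0.6 SD of the 24h change, with loss unrelated to response. Seven steps give 7 × 6 / 2 = 21 pairs. The Bonferroni critical value is then z = 3.04, and the standard error of a mean-rank difference is √(k(k+1)/(6n)) = √(56/120) = 0.68 at n = 20.

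| Analysis of the 24h change | Patients | Power |
|---|---|---|
| Signed-rank, all pairs | 26 | 81% |
| Signed-rank, completers | 20 | 70% |
| Dunn, 21 comparisons | 26 (if complete) | about 33% |
| Dunn, 6 comparisons | 20 | 32% |
| Dunn, 21 comparisons | 20 | 21% |

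Losing six patients costs about 11 points on the signed-rank scale (81% to 70%) and about 12 on the Dunn scale (33% to 21%). The remaining gap, 81 − 33 = 48 points, comes from testing the primary contrast inside a corrected seven-step procedure.

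**The case against.** The strongest reply is that Section 8 does not define its steps. The protocol also has a four-time laboratory schedule, and a Friedman analysis of the five EIT steps up to 24h would drop nobody for missing 48h or 72h. This does not carry the point. No text sets up a five-step analysis, and Section 2 also wants ventilation distribution at different times. Even on that reading, the 24h Dunn contrast has about 38% power on 26 patients, against 81% for the signed-rank test. It is true that the protocol never says in words that incomplete patients are excluded; that follows from the test it names.

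A second reply is that analysis sets and missing-data rules belong in an SAP, and Section 10.5.1 has a statistical analysis proposal confirmed before data lock. That would answer a complaint about a missing rule. Here the protocol itself fixes a test that does not fit its endpoint, and an SAP using another test for the primary outcome would depart from Section 8.

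A third is that 30 patients already allow for loss: 20 completers remain even at 33%, and entry is limited to patients expected to exceed 72 hours of APRV. As to numbers this has some force, and loss after 24h may be small. It does not answer selective loss.

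Two limits stand. Most of the power gap is due to the multiple-comparison procedure, and the count of 21 pairs is itself a reading, since Section 8 does not fix it. The bias is conditional: rate, timing, correlation and direction are all assumed.

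**Conclusion.** The concern holds. The protocol ties a 24h endpoint to a complete-block test on a schedule running to 72h, while foreseeing withdrawal and stopping study tests at dropout. The seven-step reading is the one the text supports.

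The effect of incomplete rows is modest. It is close to negligible at 10% loss (two pairs). At 33% it costs six pairs and about 11 points of power, with a possible shift of 0.11 to 0.27 SD if staying is related to response and losses run one way. The shift is nil if loss is unrelated to response or balanced. The tested 24h contrast is not prone to false positives; its weakness is low power, mostly from the 21-pair correction. The point should be fixed because the remedy is cheap and removes both problems for the primary outcome.

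**What to change.** In Section 8, name the primary analysis: a paired comparison of baseline and 24h, for example a Wilcoxon signed-rank test at two-sided 5%, in every patient with both EIT readings, whatever happens later. Keep the seven-step Friedman and Dunn analysis as secondary, for the time course. Report the number analysed and the reasons for loss at each time. Optionally, use a method for the time course that accepts incomplete rows, such as a mixed model, with its missing-at-random assumption stated.

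The cost is one or two sentences, with no extra patients, measurements or special software. There will be one more named test, and patient numbers will differ slightly between the 24h and time-course analyses. Patients lost before 24h are not recovered.

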1.4.6 Discussion

APRV is a classical mode of MV that can effectively improve oxygenation in ARDS patients. Its unique characteristic of inverse ratio ventilation helps to increase the time of alveolar gas exchange and effectively improve oxygenation. In addition, it can increase the mean airway pressure to promote the re-aeration of collapsed alveoli. Because the airway pressure is set according to the platform pressure, there is less possibility of barotrauma during APRV.

At present, the effects of APRV on respiratory physiology are mostly limited to animal experimental models of ARDS, and its effects on respiratory physiology of ARDS patients still uncertain. For instance, whether it can improve the heterogeneity of lung lesions, or promote the re-aeration of collapsed alveoli, or improve V/Q ratio in ARDS patients have not been supported by sufficient clinical evidence. EIT is a noninvasive, nonradioactive real-time bedside lung imaging tool for monitoring local alveolar ventilation. We hypothesized that EIT may help to clarify the effects of APRV on local lung ventilation, pulmonary shunt, dead space ventilation and V/Q ratio. We hope that this study will help clinicians to obtain a deeper understanding of APRV and promote its application in ARDS patients.

2. Objective and outcome

Objective: to clarify the effect of APRV on pulmonary ventilation

distribution and V/Q ratio in ARDS patients.

Primary outcome: Effect of 24h APRV on pulmonary ventilation distribution in ARDS patients.

Secondary outcome: Effects of APRV on lung ventilation distribution and V/Q ratio in ARDS patients at different times.

3. Study design

3.1 overall design

A Single center prospective observational study.

ARDS patients who received APRV were monitored by EIT at the time of before APRV and after APRV at 2h, 6h,12h,24h,48h and 72h. MV parameters, respiratory mechanics, results of arterial blood gas analysis, and hemodynamic status were recorded, and cardiac status was monitored by point-of care ultrasound.

Data collecting

- (1) Demographic data: Sex, age, height, weight.
- (2) Vital signs: Organ function including sequential organ function score (SOFA) score, acute physiology and chronic health evaluation II (APACHE II) score.

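### Dunn tests after Friedman make the 2h verdict depend on later readings, so a 2h change in all 20 patients can go undetected

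*Protocol*

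**What the plan says.** Section 8 fixes one procedure for the repeated readings: the "data obtained at each step were compared using Friedman ANOVA of repeated measurements and, when appropriate, through Dunn post hoc tests". The post hoc step is "Dunn post hoc tests using Bonferroni correction", two-sided, at the 0.05 level. Section 8 does not say which pairs of times form the Bonferroni family.

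Section 5 sets seven EIT readings, "monitored by EIT before APRV and 2h, 6h, 12h, 24h, 48h and 72h after APRV". The secondary outcome in Section 6.1 is "the effect of APRV on V/Q and pulmonary shunt at each time point monitored by EIT". Section 2 words it as "Effects of APRV on lung ventilation distribution and V/Q ratio in ARDS patients at different times". Section 3.2 states that "the number of patients is generally required to be 20" and raises enrolment to 30 to allow for losses.

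**The concern.** The secondary outcomes need a verdict at each time after APRV starts, most naturally the change from the before-APRV reading. Dunn after Friedman answers a different question, because the gap it tests depends on where the other five readings fall. If readings keep moving the same way after 2h, before and 2h hold neighbouring ranks, and a large change in every patient scores no more than a tiny one.

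At stake is the early part of the time course. Sections 1.1.1 and 1.3 raise the possibility that higher mean airway pressure increases shunt. A rise in shunt at 2h followed by a fall below the starting value is one pattern for which this test has little power.

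**Working it through.** **Inputs**
- Readings per patient: k = 7 (Section 5).
- Patients: n = 20 required, 30 enrolled (Section 3.2).
- Two-sided 0.05 with Bonferroni (Section 8).
- Number of comparisons m: not stated. Assumed range: 6 (each time against before) to 21 (all pairs, 7 × 6 / 2).
- No effect size, SD, power or expected course is given, so the figure of 20 cannot be reproduced. Steps 1 to 5 need no effect size or SD.

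**Step 1: what the statistic measures.** For one patient, the rank gap between two times is the sign of the change × (1 + number of other readings lying between them). Dunn divides the mean gap by SE = sqrt(k(k+1)/(6n)).
- n = 20: sqrt(56/120) = 0.683.
- n = 30: sqrt(56/180) = 0.558.
- Critical mean gap at n = 20: 1.96 × 0.683 = 1.34 uncorrected; 2.638 × 0.683 = 1.80 for m = 6; 3.038 × 0.683 = 2.08 for m = 21.

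**Step 2: all patients rise steadily (assumed course).** At n = 20 the rank sums are 20, 40, 60, 80, 100, 120 and 140. Friedman chi-square is 120, P = 1.6e-23, so the post hoc tests follow.

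| Contrast with before | n | Gap | z | P uncorrected | m = 6 | m = 21 |
|---|---|---|---|---|---|---|
| 2h | 20 | 1 | 1.46 | 0.143 | 0.86 | 1.0 |
| 2h | 30 | 1 | 1.79 | 0.073 | 0.44 | 1.0 |
| 6h | 20 | 2 | 2.93 | 0.0034 | 0.020 | 0.072 |
| 6h | 30 | 2 | 3.59 | 0.00034 | 0.002 | 0.007 |

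For the 6h gap of 2 with m = 21, corrected P is 0.057 at n = 21 and 0.045 at n = 22. From 12h on, the contrast with before is significant under either family. At 24h the gap is 4 and z = 5.86.

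**Step 3: same before and 2h data, different later readings.** If all five later readings lie between before and 2h, the gap is 6, z = 8.78 and P = 1.6e-18 (3.3e-17 with m = 21). The verdict at 2h reverses although nothing at 2h has changed.

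**Step 4: a test of the two readings alone.** With 20 of 20 changes in one direction, the exact two-sided P is 2 × 0.5^20 = 1.9e-6. This becomes 1.1e-5 after × 6 and 4.0e-5 after × 21, whatever the later readings are.

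**Step 5: patients needed for a unanimous one-rank gap.** n = z² × 56/6. For m = 6: 2.638² × 9.33 = 65. For m = 21: 3.038² × 9.33 = 86.1, so 87.

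**Step 6: how far this reaches beyond the unanimous case.** Simulations with n = 20 and independent normal reading errors; every course is assumed.
- Steady rise of 3 points per reading, SD 2, 3 and 4: Dunn declares a 2h change in 0% of trials at each SD. Paired signed-rank does so in 99%, 84% and 57% with Holm over six, and in 94%, 55% and 29% with Bonferroni over six.
- Early rise, then a fall below baseline: Dunn 0–3% (m = 21) or 0–8% (m = 6), against 73–100% for signed-rank with Holm.
- Step of 3 points that then stays flat, SD 3: Dunn 33% (m = 21) or 44% (m = 6), against 54% for signed-rank with Bonferroni over six and 65% with Holm.

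**The case against.** Friedman followed by Dunn is a recognised non-parametric procedure, Section 8 applies the post hoc tests only when appropriate, and the choice of contrasts is often left to the SAP. That holds for the unstated comparison family, which is why both ends are shown. It does not answer the main point: Dunn is a stated choice, and the 2h contrast fails even with no correction.

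The protocol gives no expected time course, so the worst cases rest on assumed courses. This also stands. With a 3-point step that stays flat and SD 2, Dunn with six comparisons detects the 2h change in 91% of trials, against 95% for signed-rank with Bonferroni over six. Part of the simulated gain elsewhere comes from Holm rather than from the change of test.

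Several stronger readings are tempting and not supported:
- **That 6h is missed as well.** Under a steady rise this needs all 21 pairs in the family and at most 21 analysed patients. With six comparisons or 22 patients it is detected.
- **That the test ignores the change, or gives a gap of 1 however many patients show it.** Direction is used and only size is lost. The mean gap is 1 only when every patient moves the same way; if half rise and half fall it is 0.
- **That harm would be hidden.** Section 8 reports medians with interquartile ranges, so an early rise in shunt could be seen there. Nothing in the protocol says a non-significant pair will be reported as no effect.
- **That the primary 24h result is compromised.** Under a steady rise it is safe. The same weakness reaches it only if 24h shows the smallest of the six changes (gap 1, corrected P 0.86 to 1.0).

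Finally, reading the secondary outcome as change from before APRV is an inference. It is the natural one, since the effect of APRV at a given time needs the before-APRV reading as reference, but Section 8 may also intend pairs of later times.

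**Conclusion.** The point holds, with its firmest form at 2h. As written, Section 8 can return a non-significant result at 2h when every patient has changed, with 20 or 30 patients and with or without Bonferroni. The 2h verdict also depends on later readings: from P = 0.14 to about 1e-18 uncorrected for identical 2h data. The rank arithmetic assumes complete readings and a unanimous change. How often it would matter depends on the course. The loss is near total for progressive courses or an early rise that then falls below baseline, and smaller for a flat step, where it varies with step size. This should be changed, but it bears on the secondary time course rather than on the validity of the study as a whole.

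**What to change.** In Section 8, replace the Dunn tests for the per-time-point outcomes with wording to this effect:

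> At 2h, 6h, 12h, 24h, 48h and 72h, the change from the before-APRV reading will be tested with a paired Wilcoxon signed-rank test and reported as the Hodges-Lehmann median change with its confidence interval. P values will be Holm-adjusted over the six times within each variable. The Friedman test will be reported as an overall description of the time course.

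The cost is one sentence, with no new patients, readings or procedures. Pairs of later times, such as 12h against 48h, would no longer be formally tested; no outcome in Section 2 or 6.1 names such a pair. If the investigators do want one, it should be named in advance and added to the adjusted family.

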9.1 Risk assessment of subjects in the study and risk disposal plan

(1) Reporting methods: Any adverse events, such as subjects' subjective discomfort and abnormal laboratory testing, should be treated seriously and analyzed carefully, and immediate measures should be taken to protect the safety of subjects

(2) Processing procedures: detailed records, and according to the situation of retest, record the disappearance of its continuous turnaround and other circumstances.

(3) Follow-up for unmitigated adverse events. All adverse events should be followed up until they are properly resolved or the disease is stable.

